Background: Structured diabetes self-management education (DSME) is internationally recommended for all people with newly diagnosed type 2 diabetes and is designed to support patients in self-managing their condition and prevent associated long-term complications. DSME is proven to be as effective as pharmacotherapy in preventing diabetes associated morbidity and premature mortality but attendance at both a national and local level remains poor. Local records suggest that of those that start DSME (9%) only 12.6% complete the programme. Attendance at DSME is currently benchmarked as having completed a registration form and had at least one active engagement with a programmes content, with 'completion' measured against ≥60% completion despite landmark trials reporting outcomes based on the full completion of a programme. Little is known, of the effectiveness of DSME on the psychological and emotional health of people with diabetes who complete less than the full DSME programme.

Aim: This feasibility study will test the impact of differing completion rates of a face-to-face DSME programme on patient reported outcomes measuring self-care, diabetes distress and quality of life in people with type 2 diabetes.

Methods: Using a quantitative approach, a single centre, randomised feasibility study will be conducted, aiming to recruit 120 eligible people with type 2 diabetes due to attend a secondary care diabetes clinic in the Northwest UK for specialist support, education and advice. Participants will be randomised into one of four groups: Group 1 will receive a full DSME programme, Group 2 will receive 60%, Group 3 will receive 10% and Group 4 will have delayed education. Normal clinical care will continue. Preliminary outcomes (psychometric questionnaire scores measuring ability to self-care, diabetes distress and health related quality of life) will be evaluated at baseline and 3-4 months post-intervention. Measures of feasibility (eligibility, recruitment and retention rates) will be

reported.

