6.2 Study processes

Screening and recruitment

Potentially eligible participants meeting the inclusion criteria and not excluded by exclusion criteria (outlined in section 8.1) who are either due to attend the diabetes centre for new patient clinic, have been referred for DSME intervention or are on the monthly shared care report for newly diagnosed type 2 diabetes requiring an offer of DSME will be screened for entry into the study and added to a screening log sheet (appendix 1). Potentially eligible participants due to attend new patient clinic will be invited into the study by NP clinic letter (appendix 1) with attached participant information sheet (PIS) (appendix 1). Letters will be posted ahead of their clinical appointment. For potential eligible participants identified through DSME referrals or the monthly shared care record report will be sent a telephone screening letter (Appendix 1) and PIS prior to meeting with the researcher. Study recruitment technique is outlined in further detail in section 8.2.2.

At the screening meeting potentially eligible participants will be asked to confirm they have read the PIS and invited to ask questions about the research. Where patients decline to take part in the research, they will be reassured this will not have any impact on their current or future treatment. Participants who give written informed consent will be enrolled onto the study. The researcher will utilise an informed consent checklist (Appendix 1) to ensure consistency and that all elements for informed consent have been completed. Participants will be consented for informing their GP, this is made clear in the PIS.

Visit 1

At enrolment baseline characteristics will be recorded from the electronic medical record, or where not available directly from the patient: NHS number, age, sex, ethnicity, diabetes duration, postcode, latest HbA_{1c}, prescribed glucose lowering agents, and a Charlson Comorbidity Index will be calculated. Postcode will be used to calculate indices of multiple deprivation (IMD) score.

Participants (n=120) will be randomised by permuted block strategy of 2:1 across four groups using an online randomisation software application designed for clinical trials (51,52). Due to the design of this study randomisation will not be blind to the researcher or participants. Group design will be as follows:

- Group 1: DSME 6 hours, 100% completed (completed).
- Group 2: DSME 3 hours 36 minutes, 60% completion (partial completion)

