8.2.21.2.2 Sample identification and technique

A convenience sample of 120 participants will be recruited for this study through three existing streams with potentially eligible participants added to the screening log sheet (appendix 1) and the pre-visit 1 section of the DIABETES-PRO study visit 1 pathway will be completed (appendix 1).

1. Clinic lists of new patients due to attend the diabetes centre at St Helens Hospital are available on the hospital patient administration system. The hospital electronic record will be used to screen for potentially eligible participants from the clinical list by the researcher. Potentially eligible participants due to attend new patient clinic will be invited into the study by letter (appendix 1, NP clinic screening letter) with attached PIS which will be posted ahead of their clinical appointment. On the day of their clinical appointment the researcher will meet potentially eligible participants to check they received the PIS and to answer any questions. Where potentially eligible participants agree they will be invited for

screening. Following screening, where eligible participants agree to be involved in the research and provide written informed consent, they will be enrolled in the study.

2. Patients who have been referred by their GP for DSME are called and offered education. Education referrals will be used to screen for potentially eligible participants from those awaiting a DSME appointment by the researcher. Potentially eligible participants will be asked as part of the DSME booking process if they would like information on the research. Where potential eligible participants agree a letter (appendix 1, telephone screening letter) will be sent out with a PIS and a screening appointment will be made with the researcher. Screening appointments will be offered either at the Diabetes Centre or as a home visit. Following screening, where eligible participants agree to be involved in the research and provide written informed consent, they will be enrolled in the study.

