3. Patients who have opted into data sharing and have been diagnosed with type 2 diabetes within the last month in primary care are reported via the shared care record, called and offered DSME. As part of this process potentially eligible participants will be screened and identified by the researcher. Potentially eligible participants will be asked as part of the DSME booking process if they would like information on the research. Where potential eligible participants agree a letter (appendix 1, telephone screening letter) will be sent out with a PIS and a screening appointment will be made with the researcher. Screening appointments will be offered either at the Diabetes Centre or as a home visit. Following screening, where eligible participants agree to be involved in the research and provide written informed consent, they will be enrolled in the study.

The researcher is employed as a diabetes clinical research fellow in the Diabetes Centre at St Helens Hospital and therefore already a member of the patients existing clinical team, however, is not providing direct clinical care to any potential participants. Clinical appointment lists and patient records will be obtained by the researcher in her existing NHS role. Sampling will continue until the required number of participants are recruited.

A screening and recruitment log will be stored in the study file and will include the following information: patient initials, screening outcome date of consent, if consent was refused, did/did not meet inclusion/exclusion criteria, date entered the study, unique identifier, randomisation group, study status (ongoing, withdrawn, completed, died) (70,71). A blank copy of the screening and recruitment log is included in appendix 1. Mersey and West Lancashire Teaching Hospital NHS Trust R&D department will be informed of all participants recruited to the DIABETES-PRO study.

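### As written, the screening log starts after an uncounted first eligibility check, so an eligibility rate taken from it is likely to be too high for the source lists

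*Combined protocol and SAP*

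**What the plan says.** The abstract states "Measures of feasibility (eligibility, recruitment and retention rates) will be" reported, and gives the purpose as testing whether a full randomised trial is feasible. It does not define the eligibility rate. The outcomes in section 5.2, the analysis in section 6.4 and the progression criteria in Table 3 do not mention it.

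On who enters the log, section 6.2 (Screening and recruitment) begins with "Potentially eligible participants meeting the inclusion criteria and not excluded by exclusion criteria (outlined in section 8.1") and says that such people, from the three sources, "will be screened for entry into the study and added to a screening log sheet (appendix 1"). Section 8.2.2 describes recruitment "through three existing streams with potentially eligible participants added to the screening log sheet (appendix 1"). For the clinic stream it adds: "The hospital electronic record will be used to screen for potentially eligible participants from the clinical list by the researcher". For the referral and shared care streams, the researcher likewise identifies potentially eligible people before they are asked whether they want information.

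The log's listed contents include "patient initials, screening outcome date of consent, if consent was refused, did/did not meet inclusion/exclusion criteria", followed by entry date, identifier, allocation and study status. Neither recruitment stream nor reason for ineligibility is in that list. Section 8.2.3 adds that a person found ineligible after consent is recorded in the log, which is expected only occasionally.

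Two other places describe a wider screened group. Table 2 has all type 2 patients who are referred, or registered locally and opted into data sharing. Section 8.1.1 has those meeting the inclusion criteria, with no mention of the exclusions.

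**The concern.** An eligibility rate is informative only if its denominator is the population from which a full trial would draw. Here the denominator appears to be people who have already passed a check against the same criteria. Someone removed at that check, for example for structured education in the last 12 months, need for one-to-one support or inability to attend a classroom, need not appear anywhere. The met/not met entry in the log would then capture only ineligibility discovered later.

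The quantities at stake are those a later trial team would take from this study: how many people must be listed and assessed per participant randomised, how many sites are needed, and how long recruitment takes. The three streams also differ in kind (specialist clic patients, GP referrals for education, new diagnoses), so the exclusions may fall unevenly. A pooled rate without stream would transfer poorly to a site with a different mix. Table 2 claims that the three streams give a sample representative of the local population, and that could not be checked without counts of those listed and those excluded.

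**Working it through.** **1. Is there a figure to reproduce?** No. The documents give neither an expected nor a target eligibility rate, so the check concerns the structure of the rate.

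**2. The screened or logged group, place by place.**

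| Place | Group described | Are those set aside counted? |
|---|---|---|
| 6.2 | Inclusion met and not excluded | Not stated |
| 8.2.2 | Potentially eligible, after a record or referral check | Not stated |
| Table 2 | All referred, or registered and opted in | Not stated |
| 8.1.1 | Inclusion met; exclusions not mentioned | Not stated |
| 8.2.3 | Consented, later found ineligible | Yes, in the log |

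Only the last row says that a failure is recorded at a defined step, and those people are already in the log.

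**3. Size of the bias.** Let f be the share of listed people removed before logging, and g the share of logged people later found ineligible.

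- Rate from the log = 1 − g
- Rate in the source lists = (1 − f)(1 − g)
- Ratio = 1/(1 − f); g cancels

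Neither f nor g is in the documents. With g = 5% (assumed), the log rate is 95% throughout. The last column is the number of listed people needed to randomise 120, assuming that 30% of eligible people take part: 120/(source rate × 0.30), rounded up.

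| f (assumed) | Source rate | Ratio | Listed people needed |
|---|---|---|---|
| 0% | 0.95 | 1.00 | 422 |
| 10% | 0.90 × 0.95 = 0.855 | 1.11 | 468 |
| 20% | 0.80 × 0.95 = 0.76 | 1.25 | 527 |
| 40% | 0.60 × 0.95 = 0.57 | 1.67 | 702 |

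A planner using the log rate would arrive at 422 whichever row is true. The 120 is this study's target, used only for scale.

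**4. Can f be inferred from the stated flows?** No. Section 8.2.1 gives 24 referrals and 86 new diagnoses a month, 24 + 86 = 110. The green recruitment threshold is 17 a month, and 17/110 = 15.5%. That ratio mixes eligibility with willingness to take part. The 110 also ignores overlap, omits the new-patient clinic and counts diagnoses before data-sharing opt-in. It is not an eligibility rate.

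**5. Is a large f plausible?** Of the 110, 86/110 = 78% are new diagnoses, in whom a different diabetes type or recent education should be uncommon. Removing 40% of 110 means 44 people. Even if all 24 referrals were ineligible, 44 − 24 = 20 of the 86 (23%) would also have to go. Nothing in the documents supports a share that high, and nothing rules it out.

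**The case against.** The strongest reply is that section 6.2 is loosely drafted. The same sentence says these people are still to be screened, which would be pointless if eligibility were settled. The log has a field for "did/did not meet inclusion/exclusion criteria", failures after consent are recorded, and Table 2 describes wider screening. The log template is in a separate appendix that was not available, and the listed contents need not be exhaustive, so stream or reason might be there. Clinic lists, referral counts and diagnosis counts also exist elsewhere, so list totals might be recovered.

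Part of this stands. It cannot be said that ineligible people never reach the log, or that the rate will come out near 100% whatever the truth. A reader might infer that from section 6.2 alone, but the met/not met field and the wider descriptions do not support it. It also cannot be said that stream is unrecoverable.

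The reply does not supply a denominator. The met/not met field describes people already in the log. Table 2 does not say that the wider group is logged. A fuller template would not by itself settle who is entered in it. List totals recovered later would not show how many failed which criterion.

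It is also fair that eligibility is named only in the abstract and that no progression decision rests on it. That limits the weight of the point.

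**Conclusion.** The concern holds in limited form. If the plan is followed as written, an eligibility rate taken from the log has a filtered and inconsistently described denominator, and is likely to be biased upward for the source lists by 1/(1 − f). The size is unknown; the factors of 1.11, 1.25 and 1.67 rest on assumed values of f. If nobody is removed before logging there is no bias, but the log as described could not show that.

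A reader might go further and infer that a full trial could not be sized from this study. The documents do not support that. An eligibility rate does not enter a sample-size formula, which needs variability, target effect and retention. The monthly recruitment and retention criteria in Table 3 are counted independently of the log's denominator. What is weakened is planning of numbers to approach, sites and recruitment time. The point is worth correcting because the change is cheap and alters a result the study promises to report.

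**What to change.** - In sections 6.2 and 8.2.2, count everyone on each source list (new-patient clinic list, education referrals, shared care report) from the first record check. An anonymous tally is enough for those set aside.
- Record recruitment stream and first failed criterion for each person counted.
- Define eligibility rate = eligible/listed and recruitment rate = randomised/eligible, and report both by stream in section 6.4.
- Reconcile section 6.2 (including Table 2), section 8.1.1 and section 8.2.2 so that they describe the same screened group and the same point of entry to the log.

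The cost is a small wording amendment, two additional items if the log template lacks them, and a modest number of extra tallies each month from lists the researcher already reviews. At an assumed f of 40% of the 110 people a month in the two streams with stated flows, that is 0.40 × 110 = 44 tallies; at 10% it is 11. No extra staff or patient contact is needed. It should be in place before screening starts, since reasons for exclusion not recorded at the time may be hard to reconstruct.

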Contact for Clinical Queries	
[name]* Mersey & West Lancashire Teaching Hospitals NHS Trust, Diabetes Centre St Helens Hospital [name]
 
PA: [name] Email: [contact]

Sponsor	
The University of Liverpool is the research Sponsor for this Study. It is recognised that as an employee of the University the Chief Investigator has been delegated specific duties, as detailed in the Sponsorship Approval letter.
 
For further information regarding the sponsorship conditions, please contact:
 
[name] Senior Clinical Research Governance Manager [contact]

Key Protocol Contributors	
[name]* Email: [contact]
 
[name]* Email: [contact]

Committees	
This research proposal will be submitted to IRAS for independent ethical opinion by the Health Research Authority.
 
University of Liverpool Committee on Research Ethics** (online ethical approval process completed – confirmed that IRAS approval required)

*CV in appendix 1. ** University of Liverpool research ethics application project ID 13707.

Study Summary

Study Design	Quantitative feasibility study
Study Participants	People with type 2 diabetes mellitus
Planned Size of Sample (if applicable)	
120 people with type 2 diabetes.
 
Participants will be randomised across four groups, each with 30 participants.

Follow up duration (if applicable)	4 months
Planned Study Period	
This is educational research which is being undertaken to fulfil the requirements of a 3-year full time PhD with University of Liverpool commencing November 2023.
 
GANNT chart detailing timetable of research activities in appendix

	1.
Research Question/Aim(s)	
Aims
 
Using a quantitative approach this feasibility study aims to explore if patients who attend minimal aspects (10%) of diabetes self-management education (DSME) programmes gain clinically significant improvements in ability to self-care compared to those who do not attend. If the nationally accepted 60 % completion rate is as effective as 100% completion, and if
 
Research question
 
1. What is the impact of differing completion rates of DSME programmes on ability to self-care (primary outcome), diabetes distress and health related quality of life in type 2 diabetes.

Abstract

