Patient group 
 • Who is receiving the intervention? • How many patients are being seen? • Characteristics of the patients? 	
Patients with type 2 diabetes referred to the Diabetes Centre, St Helens Hospital for specialist intervention and / or DSME and / or registered with a St Helens GP and opted into data sharing will be screened for entry.
 
The Diabetes department works closely with primary care colleagues to offer specialist advice, education, and guidance to patients with diabetes who are assessed and then discharged for clinical management by their GP. Referrals for DSME are made directly from primary care into DSME education sessions. The shared care report highlights any patient with a local GP who has had a first use of a type 2 diabetes code within the last month and have opted into data sharing. The use of the three recruitment streams for this study allows for a sample which is representative of the local population and is not limited to only patients requiring specialist led care.
 
The DIABETES PRO study will aim to recruit 120 participants which will be randomised across four groups containing 30 participants each.
 
Patients ≥18 years of age from a variety of socioeconomic backgrounds. St Helens has a predominantly white British population (96.5%), and this is likely to be represented in the sample (37).

Workforce and staffing 
 • Staffing skill, grade and 	
The researcher is employed by the Diabetes Centre as a clinical research fellow and is a Fellow of the HEA with experience teaching

profession • Staff new or existing • Training needed to deploy the intervention?	adult learners within higher education settings. The researcher has a clinical background as a podiatrist and is currently registered with the HCPC. The researcher is the patient education lead within the department and is in the process of accrediting the DSME programme with QISMET.

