8.2 Recruitment

8.2.1 Sample Size

A sample size of 24-50 participants per group is deemed adequate within a feasibility study to estimate effect sizes and inform future DSME modifications and research (68,69). A sample of 120 patients will be enrolled onto this study allowing for adequate numbers (n=30) across the four groups, controlling for expected participant drop out. Monthly recruitment targets are pre-specified in a study progression criteria table (table 3) to ensure an adequate sample size is achieved for data analysis.

The diabetes outpatient department receives on average 24 referrals for DSME per month with a mean monthly attendance rate of 21 patients. Locally an average of 86 patients are newly diagnosed with type 2 diabetes each month (20), patients who have opted in for data sharing are contacted with an offer of DSME. This has been used to inform realistic recruitment rates. Recruitment rates will be kept under review and discussed with supervisors should the monthly figure fall below projected numbers.

Table 3:Progression criteria and study status

Criterion	Green	Amber	Red
Monthly recruitment	≥ 17 participants	14-16 participants	< 13 participants
Retention rate	>80% at endpoint	60-80% at endpoint	<60% at endpoint

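### The randomisation ratio is written as 2:1 for four groups, which defines no four-arm allocation and conflicts with 30 participants per group

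*Combined protocol and SAP*

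**What the plan says.** Section 6.2, under Visit 1, gives the allocation method: "Participants (n=120) will be randomised by permuted block strategy of 2:1 across four groups", using an online randomisation application. It gives no four-part ratio, does not say which groups take the 2 and which the 1, and states no block size.

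Three other places give the group sizes:

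- Study Summary: "Participants will be randomised across four groups, each with 30 participants".
- Table 2 in section 6.2, patient group row: "The DIABETES PRO study will aim to recruit 120 participants which will be randomised across four groups containing 30 participants each".
- Section 8.2.1: the enrolment of 120 is described as "allowing for adequate numbers (n=30) across the four groups, controlling for expected participant drop out".

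Section 8.2.1 also sets the standard for the group size: "A sample size of 24-50 participants per group is deemed adequate within a feasibility study". Table 3 makes retention green at ">80% at endpoint", amber at 60-80% and red below 60%. The Abstract confirms four separate arms: "Group 1 will receive a full DSME programme, Group 2 will receive 60%, Group 3 will receive 10% and Group 4 will have delayed education".

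The amendment history in Appendix 2 does not mention allocation, so the 2:1 wording is current text in version 1.1.0.

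**The concern.** There are two faults. The instruction is incomplete, because two numbers cannot define the shares of four arms. It is also inconsistent, because every way of completing it gives unequal groups, while the rest of the protocol requires equal ones.

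The allocation ratio is not descriptive text. It must be entered into the randomisation software, and allocations already made under a wrong setting cannot be undone. Section 8.2.1 presents 30 per group as leaving room for dropout within an adequate range that starts at 24. An unequal setting would shrink or remove that room in the smallest arm. It would also change a participant's chance of being allocated to delayed education: 25% under equal allocation, but anywhere from 1/7 (14%) under 2:2:2:1 with Group 4 as the small arm to 2/3 (67%) if the delayed arm took the 2 against the pooled education arms.

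**Working it through.** **Inputs.** N = 120 and four arms (Abstract, Study Summary); 30 per group (Study Summary, Table 2, section 8.2.1); adequate range 24-50 per group (section 8.2.1); retention boundaries 80% and 60% (Table 3). The plan states no expected dropout rate, so losses of 20% and 40% (100% minus each boundary) are assumptions.

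**Step 1: reproduce the plan's figure.** Arm size = N × wᵢ / Σw. With 1:1:1:1, 120 × 1/4 = 30. The stated 30 per group reproduces exactly.

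**Step 2: can any 2:1 reading give 30 per group?** If 2 and 1 are weights for individual arms, equal groups need equal weights, so a set containing both values cannot give them. If 2:1 compares k pooled groups with the other 4 − k, equal arms need k:(4 − k), that is 1:3, 2:2 or 3:1. None of these is 2:1. So no such reading fits.

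**Step 3: arm sizes and the smallest arm after loss.** Loss tolerated before the smallest arm falls below 24 is 1 − 24/n; arm size after loss is n × 0.8 or n × 0.6.

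| Reading | Arm sizes from 120 | Loss tolerated, smallest arm | Smallest after 20% loss | Smallest after 40% loss |
|---|---|---|---|---|
| 1:1:1:1 | 30/30/30/30 | 1 − 24/30 = 20% | 24.0 | 18.0 |
| Three education arms pooled v delayed, 2:1 | 26.7/26.7/26.7/40 | 1 − 24/26.7 = 10% | 21.3 | 16.0 |
| 2:1:1:1 | 48/24/24/24 | 1 − 24/24 = 0% | 19.2 | 14.4 |
| 2:2:1:1 | 40/40/20/20 | starts below 24 | 16.0 | 12.0 |
| 2:2:2:1 | 34.3/34.3/34.3/17.1 | starts below 24 | 13.7 | 10.3 |
| Delayed v three education arms pooled, 2:1 | 80/13.3/13.3/13.3 | starts below 24 | 10.7 | 8.0 |

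The last row is the least natural reading, but the text does not exclude it. The 2:2:2:1 reading does not fit whole blocks either: 120 = 17 × 7 + 1.

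**Step 4: precision of a two-arm contrast.** Relative standard error against 30 v 30 is √(1/a + 1/b) / √(2/30), assuming a common SD.

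- Larger: 27 v 27, 1.06; 40 v 20, 1.06; 24 v 24, 1.12; 34 v 17, 1.15; 20 v 20, 1.22.
- Smaller: 48 v 24, 0.97; 27 v 40, 0.97; 34 v 34, 0.94; 40 v 40, 0.87.

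The change runs from 13% smaller to 22% larger over these contrasts. Its direction depends on which groups get the larger share, which the text does not say.

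**The case against.** The strongest reply is that this is an evident slip. Three statements agree on four groups of 30, and nothing shows that the software was set to anything else. Figure 1 is not shown in the text reviewed and Appendix 1 is supplied separately, so the working setting may well be correct. That is fair, and the harm is conditional on the setting. It does not rescue the sentence: the conflicting figure sits in the one place that specifies the randomisation, and nothing in the available text corrects it.

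A second reply is that 2:1 may be a garbled description of the blocks, for example sizes 8 and 4, which are compatible with equal groups. This is speculative. If true, section 6.2 would then state no allocation ratio at all, and the same correction would be needed.

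Third, section 8.2.1 does not say that 24 must remain after dropout. Treating 24 as a floor is an inference from placing the range beside the dropout allowance. If the range refers to enrolled numbers, 48/24/24/24 and 27/27/27/40 both lie within it, while the other unequal readings do not. This limits the consequence, not the contradiction.

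Fourth, retention is not the analysed number. Section 6.4 also removes participants who do not complete their allocated education, so even equal arms at 80% retention could have fewer than 24 analysed. This stands. It is a reason not to start any arm smaller than intended.

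Finally, section 6.1 says the study is not powered. The point makes no claim about power.

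**Conclusion.** The concern holds. The ratio as written defines no four-arm allocation, and no 2:1 reading delivers the 30 per group stated in three other places; only 1:1:1:1 does. Under the four more natural unequal readings, the smallest arm starts at about 17 to 27 instead of 30. It ends at about 14 to 21 instead of 24 with 20% loss, and at about 10 to 16 instead of 18 with 40% loss. The reverse pooled reading would be lower still, at about 11 and 8.

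The contradiction rests on no assumption. Its consequences rest on three: that the software is set from section 6.2, that losses are as assumed and equal across arms, and that 24 is a minimum to be kept after dropout. The ratio governs the conduct of the trial, so it must be corrected even though equal groups are the likely intent.

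**What to change.** In section 6.2, replace the 2:1 wording with 1:1:1:1 across the four groups, after the sponsor confirms that equal allocation was intended. Check that the randomisation software carries the same ratio.

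If anyone has already been randomised under another ratio, correct it prospectively by amendment and report the numbers allocated under each ratio. The correction would not by itself restore 30 per group. For example, 60 participants at 2:1:1:1 (24/12/12/12) followed by 60 at 1:1:1:1 (15 each) gives 39/27/27/27. In that case the analysis should also account for the allocation period, because the ratio would have changed with calendar time.

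Separately, and optionally: the researcher who enrols is not blinded, so randomly varying block sizes in multiples of 4, held in a restricted document, would make the next allocation harder to predict.

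The cost is a one-sentence amendment agreed as section 10.5 describes and approved by the sponsor, with REC submission if it is judged substantial, plus a check of one software setting.
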